8.4.2 UNANTICIPATED PROBLEM REPORTING

The investigator will report all medically relevant UPs to **principal investigator (PI)**, Sponsor, the DSMB and the reviewing IRB. The UP report will include the following information:

- Protocol identification information including protocol title and number, Pl's name, and the IRB project number
- A detailed description of the event, incident, experience, or outcome
- An explanation of the basis for determining that the event, incident, experience, or outcome represents an UP
- A description of any changes to the protocol or other corrective actions that have been taken or are proposed in response to the UP

To satisfy the requirement for prompt reporting, UPs will be reported using the following timeline:

- UPs that are SAEs will be reported to the IRB and to the DCC/study sponsor within 24 h of the investigator becoming aware of the event
- Any other UPs will be reported to the IRB and to the study sponsor within 7 days of the investigator becoming aware of the problem

 All UPs should be reported to appropriate institutional officials (as required by an institution's written reporting procedures), the supporting agency head (or designee), and the OHRP within 15 days of the IRB's receipt of the report of the problem from the investigator

8.4.3 REPORTING UNANTICIPATED PROBLEMS TO PARTICIPANTS

Not applicable

9 STATISTICAL CONSIDERATIONS

9.1 STATISTICAL HYPOTHESES

The main hypothesis to be tested in this study is the superiority of at least one dose of active versus placebo on the change from baseline of the 400 m gait speed criterion after 6 months of treatment.

In order to deal with the multiplicity issue due to the two doses, a Hochberg procedure will be used for testing the main hypothesis.

Full details of the analysis and the procedure will be given in the statistical analyses plan (SAP) of the study.

9.2 SAMPLE SIZE DETERMINATION

Originally, the sample size was calculated for a comparison test at a 0.05 two-sided significance level, a power of 80%, to detect a difference of 0.05 m/s (minimal clinically important difference) between active groups and placebo on the change from baseline in the 400 m gait speed at 6 months, with a standard deviation of 0.13 (estimated from the VIVE2 trial, Fielding et al, 2017⁶²).

After analysis of the preliminary data from our observational trial data (SARA-OBS, with approx. 105 completers), the following were learned:

- During the 6 months follow-up, this study population deteriorated as suggested by a decreased gait speed of 0.05 meter per second on the 400MW test, with a standard deviation of the change from baseline of 0.2
- The expected effect of BIO101 remains at 0.05 meter per second, as the change from baseline
- Together, this new information allows an increase of up to 0.1 m/s to be considered as a minimal clinically important difference of changes at the M6 visit from baseline between the treatment groups. Under these assumptions, a number of 64 patients/group is needed, giving a new sample-size of 192 patients for 3 arms, with a standard deviation of 0.20 (estimated from SARA-OBS preliminary data).

Taking into consideration this increased expected difference between treatment arms, a formal interim analysis will be performed by the DSMB when half subjects reach their month 6 visit (See section 9.4.6). Once half study participants complete their End-of intervention study visit, an unblinded 'promising zone' interim analysis will take place and determine if there is a need to increase the sample size based on the complete efficacy data.

Based on current calculation and given a limited 20% provision for premature withdrawals or lost-to-follow up, a total number of 231 participants will be included in the study.

It is expected, that due to COVID-19 related restrictions, that the number of non-evaluable withdrawals will be higher than 20%. However, reassessment of the sample size, will take place, as a part of the interim analysis, that will take place after restrictions are lifted.

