A predefined subgroup efficacy analysis will also be performed on a number of pre-identified, at-high risk of worsening, subpopulations:

- Low gait speed
- Sarcopenic obesity
- Study participants with a chair stand sub-score of ≤2 of the SPPB
- Study participants who experience a deterioration in their ALM/BMI, as measured by the DEXA scan in the M6 visit and compared to the baseline measurement

Subgroup analyses will be provided through a forest-plot approach.

General Objectives:

- To evaluate the safety and efficacy of two doses of BIO101 (175 mg b.i.d. and 350 mg b.i.d.) orally administered for 26 weeks versus placebo in a population of community dwelling older men and women (aged ≥ 65 years) living at home and at risk of mobility disability.
- 2. To estimate treatment effect on improvement of physical function after a six-month treatment versus placebo in the target population.
- 3. To estimate treatment effect on reduced risk of mobility disability after a six-month treatment versus placebo in the target population.

Primary Objective:

 To evaluate the effect of two daily doses of BIO101 versus placebo on mobility function as measured by gait speed using the 400MW test. The absolute change from baseline in m/s observed in each treatment group at M6 will be compared to the placebo group. A minimum clinically significant benefit is set at 0.05 m/s in the mean difference between groups from M6

Objectives:

compared to baseline. The preliminary data from the SARA observational study (SARA-OBS) suggests that the untreated population naturally experienced a deterioration of 0.05 meter per second, when compared at M6 to baseline. Taken together, this increases the expected difference between treatment and placebo groups to 0.1 meter per second at M6 – corresponding to what is considered a clinically significant difference.

Key Secondary Objectives:

- a. To compare the change from baseline of a standardized patient reported outcome (PRO): the PF-10 sub-score of the SF-36. A minimum clinically significant benefit is set at 2-point difference of the change at M6 from baseline versus placebo in the mean difference between groups.
- b. To compare the change from baseline to month 6 of the muscle strength using the handgrip strength test. A minimum clinically significant benefit is set at 2 kg difference of the change at M6 from baseline versus placebo in the mean difference between groups.

Other Secondary Objectives:

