3 OBJECTIVES AND ENDPOINTS

The overarching objective of the SARA-INT clinical trial is to evaluate the efficacy and safety of BIO101 26-week oral administration on the prevention of mobility disability in at-risk, community dwelling older adults (\geq 65 years) reporting a loss of physical function over the last 6-12 months. In particular, this trial aims to:

- a. Estimate treatment effect on improvement of physical functions after a six-month treatment versus placebo in the target population.
- b. Estimate treatment effect on decrease of risk of mobility disability after a six-month treatment versus placebo in the target population.

OBJECTIVES	ENDPOINTS	JUSTIFICATION FOR ENDPOINTS
Primary		
To evaluate the effects of two daily doses of BIO101 versus placebo on mobility functions as measured by the gait speed during the 400MW test.	The primary endpoint is the 400MW test gait speed: the change from baseline to month 6/month 9 will be compared between groups of treatment (each dose versus placebo). The absolute change from baseline in meters per second observed in each treatment group at M6 /M9 will be compared to the one observed in the placebo group. A minimum clinically significant benefit is set at 0.1 m/s in the mean difference between groups.	This endpoint was chosen because it is a continuous variable that reliably expresses the grade of residual (lower limbs) muscle functions in older adults. The 400MW test gait speed was shown to improve after 6months of structured physical activity (Santanasto et al, 2017 ¹⁶). This test could also be applied as a dichotomous variable but this would necessitate a much longer observation period not corresponding to the phase 2 operational requirements. The 400MW test gait speed change following a 6-month intervention has been demonstrated as a good predictor of mobility disability progression or improvement during the LIFE study according to Santanasto et al., 2017 ¹⁶ . A change of 0.05 m/sec was considered a minimal clinically meaningful change to patients, according to Perera et al, 2006 ³⁶ , and is well adapted to a phase 2 design. In addition, with our analysis of a similar study population in our phase 2a, observational study, (SARA-OBS), a decline of 0.05 m/s over the 26-week period was detected. Therefore, this observation allows an increase of an additional 0.5 m/s for the expected

OBJECTIVES	ENDPOINTS	JUSTIFICATION FOR ENDPOINTS

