		difference between the treatment groups and hence 0.1 m/s was chosen as the minimal clinically meaningful change for this study. A change of 0.1 m/sec will also be considered as a substantial clinically meaningful change to patients ³⁶ , and will be used for (individual) responders analysis.
Key Secondary:		
 To evaluate the effect of BIO101 on physical function from the study participants' perspective using an adapted PRO. To evaluate the effect of BIO101 on muscle strength using the handgrip strength test. 	 The PF-10 sub-score of the SF-36: the change from baseline to month 6/month 9 will be compared between groups of treatment (each dose versus placebo). Additionally, a responder analysis will be performed with a responder definition of "patient with an improvement of PF10 greater or equal to 2 points versus baseline", at an individual level. Handgrip strength test: the change from baseline to month 6/month 9 will be compared between groups of treatment, each dose versus placebo; a minimal clinically significant benefit is set at 2 kg of difference between groups. 	The SF-36 is a validated measure of health-related quality of life, sensitive to significant treatment effects, addressing health concepts that are relevant to the patients' perspectives. Specifically, the PF-10 has been used in numerous clinical trials and is considered a simple yet effective measure of mobility disability and also for epidemiological studies ³⁶ . Climbing one flight of stairs (no change versus decline of two levels, two-point difference) or walking a block (no change versus two levels decline) exemplifies a substantial meaningful change, as appreciated by patients ³⁶ . Change in muscle strength is directly related to the expected mechanism of action of the investigational drug and needs to be assessed. Assessment of muscle strength using the handgrip strength test is commonly used in interventional studies targeting muscle loss in older adults ^{21,23}
Other secondary		

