This test also provides a dichotomous result (i.e., capacity/incapacity to complete the task) that accurately reflects a specific and clinically relevant condition, which is mobility disability¹. The ability to walk 400 m is a proxy for mobility within the community and independent living¹⁶. As opposed to walking tests aimed at measuring the reserve capabilities of an individual (e.g. 6MWT), the 400MW test is very safe and does not need to be performed as fast as possible. On the other hand, the relatively long distance walked allows identification of those individuals with mobility limitation but who may appear to be well functioning during shorter tests (e.g., 4 meters). The 15-minute time limit of the 400MW test is indeed there to differentiate the mobility efficiency of the individual. The inability to complete the 400MW test has already been used as the defining criterion for mobility disability in major clinical trials, in particular the LIFE-P and full-scale projects^{15,30}. It has been demonstrated that the capacity of the 400MWtest to predict major negative health-related events (including disability and mortality) is independent of comorbidities.

A difference of change from baseline of 0.1 m/s is determined to be the minimal clinically meaningful change between treatment groups based on preliminary analysis of the SARA-OBS participants, and a change of 0.1 m/sec will also be considered as a substantial clinically meaningful change to patients, according to Perera et al, 2006³⁶.

6 Minute Walking Test (6MWT)

The 6MWT is a test for functional exercise capacity and involves measuring the distance a participant can cover within the allotted time of 6 minutes.

The 6MWT has gained importance in the assessment of functional exercise capacity in patients with chronic respiratory disease. It has been used in many studies with elderly people. The 6MWT has proved to be reliable, inexpensive, safe and easy to apply^{43,44}. In addition, it correlates well with important outcomes including death^{45,46}. Considerable variability was observed in the

distance walked in the 6MWT in studies performed by healthy volunteers^{46,47}. The study performed with healthy elderly study participants aged 50-85 years⁴⁷ showed that the 6MWT distance ranged from 383 to 820 m. On average, the distance was 631 ± 93 m. An important part of the variability in 6MWT was explained by height, gender, age and weight as dependent variables.

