8.7.2 Analysis of primary efficacy endpoint

The 400MW test used to calculate the 400MW gait speed will be performed at Screening, M3, M6/M9 and last assessment on treatment visits. The Screening value will be considered to be the baseline value. If the screening value is missing the baseline value will be considered as missing.

The main analysis of the primary endpoint (change from baseline to month 6 (M6)/month 9 (M9) in 400MW gait speed) will be performed using the FAS.

Change from baseline to M6/M9 in 400WM gait speed will be summarized by treatment group.

The main hypothesis to be tested in this study is the superiority of at least one dose of active versus placebo on the change from baseline in 400m gait speed after 6 months of treatment.

The null hypotheses H_{01} and H_{02} given below will be tested against the alternative hypotheses H_{A1} and H_{A2} respectively:

$$\begin{split} &H_{01}\!\!:\ \mu_1 - \mu_P \!<\! 0.1, \qquad H_{02}\!\!:\ \mu_2 - \mu_P \!<\! 0.1, \\ &H_{A1}\!\!:\ \mu_1 - \mu_P \geqslant 0.1, \qquad H_{A2}\!\!:\ \mu_2 - \mu_P \geqslant 0.1, \end{split}$$

Where μ_1 and μ_2 denote the mean change from baseline in meters per second in the 400MW gait speed at M6/M9 in the 175 mg BIO101 and 350 mg BIO101 groups. With μ_p denoting the mean change from baseline at M6/M9 in the placebo group. A minimum clinically significant benefit is set at 0.1 meter per second in the mean difference between groups (i.e., superiority margin).

A Mixed Effect Model Repeat Measurement (MMRM) model with fixed factors treatment and center and the baseline score and the stratification factor (gender) will produce an estimate of the contrast at M6/M9 in the change from baseline of the 400MW test gait speed between each active arm and the placebo group (section 8.7.1.1) (after adjustment by the Hochberg procedure (Section 8.7.1.6)).

The same MMRM model will be also fitted for the Per-Protocol population to give an estimand of the efficacy of 175mg BIO101 and 350mg BIO101 in the population with a good compliance to the protocol. The FAS is the main population/set of interest.

A by-subject listing of 400MW data will be provided.

Alternative methods to adjudicate missing data for the primary endpoint like the Bayesian Multiple Imputation (MI) methods will also be considered. Chen at al (2017) demonstrated the interest of applying Bayesian MI method to 400MW non-completers in the LIFE study⁹. More detail please refer to section 8.7.6.

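### The minimum important difference in gait speed is 0.05 m/s in the synopsis and 0.1 m/s elsewhere; the 0.1 is derived as an expected difference, and SAP 8.7.2 turns it into a superiority margin

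*Protocol*

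**What the plan says.** The threshold appears in current text at two values.

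- Protocol 1.1 (synopsis, primary objective): "A minimum clinically significant benefit is set at 0.05 m/s in the mean difference between groups from M6". The same paragraph then adds the decline seen in SARA-OBS and calls the resulting 0.1 m/s the expected difference.
- Protocol 3, endpoint column: "A minimum clinically significant benefit is set at 0.1 m/s in the mean difference between groups". The justification column ends: "0.1 m/s was chosen as the minimal clinically meaningful change for this study".
- Protocol 8.1: "A difference of change from baseline of 0.1 m/s is determined to be the minimal clinically meaningful change between treatment groups".
- Protocol 9.2: "Together, this new information allows an increase of up to 0.1 m/s to be considered as a minimal clinically important difference". The next paragraph of 9.2 refers to the same 0.1 as an increased expected difference.
- SAP 8.7.2: "A minimum clinically significant benefit is set at 0.1 meter per second in the mean difference between groups (i.e., superiority margin"). The hypotheses printed there are H0: difference < 0.1 against HA: difference ≥ 0.1, for each dose.

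On what patients notice, section 3 says: "A change of 0.05 m/sec was considered a minimal clinically meaningful change to patients". Sections 3 and 8.1 describe 0.1 m/s as a substantial change.

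The 0.05 m/s in the opening paragraph of protocol 9.2 and in SAP 5 is introduced as the original basis. It is history and not part of the conflict. However, SAP 5 never gives the revised basis (0.10, SD 0.20) for the 231 participants it quotes.

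**The concern.** A minimum important difference says what matters to patients. A planning difference says what the sponsor expects to see. A decline on placebo can raise the second, but it gives no reason to raise the first. Section 9.2 gives the sum of decline and drug effect both names.

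Two things are at stake. First, an observed difference between about 0.07 and 0.10 m/s would be significant against zero and would exceed the synopsis minimum, yet fall short of the minimum in sections 3 and 8.1 and the SAP. Two readers could reach opposite conclusions on relevance. Second, and more serious, the label has moved into the SAP's primary hypotheses as a margin, which is a different and far harder test from the one the trial was sized for.

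**Working it through.** **Inputs.** From protocol 9.2: planning difference 0.10 m/s, SD 0.20, 64 per group, 192 for three arms. Two-sided 0.05 and 80% power are stated there for the original calculation; I assume they carry over, which the match in step 1 supports.

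**1. The plan's own figure.** Standardised difference = 0.10/0.20 = 0.5. The normal approximation, n = 2(1.960 + 0.842)²/0.5², gives 63 per arm. The two-sample t-test gives 63.77, rounded up to 64, so the stated figure is reproduced. Power at 64 per arm is 80.1%.

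**2. How 0.1 arises.** Untreated decline 0.05 + assumed drug effect 0.05 = 0.10. In the original calculation the 0.05 was a difference between active and placebo. In the revised text it is said to remain 0.05 but is now a change from baseline, and the decline is added to it. As an expectation this can be argued: active +0.05, placebo −0.05, difference 0.10. Nothing in it bears on the smallest difference worth having. (Section 3 prints the increment as 0.5 m/s, evidently meant as 0.05.)

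**3. Power for the synopsis minimum.** With SD 0.20 and 64 per arm, t-test at two-sided 0.05, tested against zero:

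| True difference | Power |
|---|---|
| 0.10 m/s | 80.1% |
| 0.05 m/s | 28.9% |

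Under Hochberg, by simulation with 64 per arm, the chance that at least one dose is significant is about 32% to 33% if both doses give 0.05 and about 22% if only one does. With 77 per arm and no dropout, unadjusted power for 0.05 is 34%.

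**4. Smallest significant difference.** Standard error = 0.20 × √(2/64) = 0.0354. Times t(126; 0.975) = 1.979, this gives 0.070 m/s.

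**5. SAP 8.7.2 read literally.** Shift the null to 0.1, keeping the same standard error and a two-sided 0.05 level (0.025 in the favourable direction). Power depends on (true difference − 0.1)/0.0354:

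| True difference | Power against a margin of 0.1 |
|---|---|
| 0.10 m/s | 2.5% |
| 0.15 m/s | 29% |
| 0.20 m/s | about 80% |

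So at the very difference the trial was planned for, the printed hypotheses would be rejected only at the false-positive rate. Eighty per cent power would need a true difference of about 0.2 m/s, twice the planning value.

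**6. What the other sections test.** Protocol 9.1 states superiority of at least one dose over placebo with no margin. SAP 8.7.1.6 calls the study positive when at least one dose is significantly better than placebo. SAP 8.7.2 itself states plain superiority just before printing the 0.1 hypotheses. The ANCOVA and logistic contrasts in SAP Appendix A are against zero.

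**The case against.** **0.1 has other support.** This stands in part. A reader might infer that the sum is the only reason offered for 0.1. It is not: the synopsis says 0.1 corresponds to a clinically significant difference, and sections 3 and 8.1 cite a published source for 0.1 as a substantial change. But that supports 0.1 as an important change, not as the smallest one, and section 3 gives the minimal label to 0.05.

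**The synopsis may simply be an incomplete update.** This is plausible. The protocol's summary of changes lists the synopsis among the sections where the minimum benefit moved to 0.1. It is therefore tempting to infer that 0.05 is the true minimum, or that 0.1 is. The documents settle neither; the choice rests on a cited source not available here and is for the sponsor to justify.

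**No operative rule compares the result with 0.05 or 0.1.** Largely right. Success is judged by p-values against placebo, and the individual responder cut-off is 0.1 throughout. A reader might take the conflicting minimum for the trial's decision threshold, which goes too far. The exception is SAP 8.7.2, where 0.1 enters the hypotheses.

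**Powering on an expected difference is legitimate, and the expectation is disclosed.** Agreed. The 29% is also before any interim increase. At the protocol 9.4.7 maximum of 330 (110 per arm, all evaluable) power for 0.05 would be about 45% to 46%. Whether that increase still applies is unclear, since SAP 8.10 marks the interim analysis as not applicable while the SAP's list of changes defers its details to a separate document.

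**Conclusion.** The point holds as a labelling conflict with one operative consequence. The between-group minimum differs by a factor of two between the synopsis and sections 3, 8.1, 9.2 and SAP 8.7.2, and the higher value is derived as an expected difference. The consequence is the margin in SAP 8.7.2, which contradicts protocol 9.1 and SAP 8.7.1.6 and, taken literally, leaves about 2.5% power at the planning difference.

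The documents do not support the stronger reading that the sample size is wrong: 64 per group is correct for 0.10 m/s with SD 0.20. What is missing is a statement that the same 64 give only about 29% power for 0.05 m/s.

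The figures assume SD 0.20, 64 evaluable per arm, an unadjusted two-sided 0.05 level except where Hochberg is named, and no interim increase.

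**What to change.** 1. In SAP 8.7.2, restate each null hypothesis as no difference from placebo (difference = 0), in line with protocol 9.1, and delete the parenthesis naming a superiority margin. Deleting the parenthesis alone is not enough, because the printed null of < 0.1 would remain.
2. In protocol section 3 (endpoint and justification columns), 8.1 and 9.2, and in SAP 8.7.2, label 0.10 m/s as the expected (planning) difference.
3. State one minimum important difference, with its justification, in every place including the synopsis. The documents' own patient-level anchor for a minimal change is 0.05 m/s. If the sponsor prefers 0.1, it needs a patient-based reason and must reconcile it with section 3, which calls 0.05 minimal and 0.1 substantial.
4. In protocol 9.2 and SAP 5, state the planning basis (0.10 m/s, SD 0.20, 64 per arm, 80% power) and add that power for 0.05 m/s is about 29%, unadjusted and before any interim sample size increase.

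The cost is wording in the sections named and one less favourable power figure. No patients are added. The SAP changes should be made before unblinding.
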